10.3 Primary Study Hypothesis

The study hypotheses for the primary objective are:

- Coitus will not impact the pharmacokinetics of TFV following a single precoital dose, BAT or multiple applications of study product

- Coitus will not alter the antiviral activity in genital tract secretions following single pre-coital dose, BAT or multiple applications of study product

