The difference in drug concentration levels at the visits where the female participants dose with gel and engage in coitus vs. the visits where female participants dose with gel and do not engage in coitus will be analyzed using the paired t-test or Wilcoxon signed-ranks test, as appropriate. In Group 1, for assessment of the BAT dosing regimen, DC from the visit where female participants perform BAT dosing with gel, coitus, and post-coitus gel will be compared to DC from the visit where female participants dose with gel (-1 hour) and do not engage in coitus. The BAT DC will also be compared to the visit where female participants dose with gel (-1 hour) and engage in coitus.

For each of the nine (9) assessments, the estimate of the mean percentage change along with the corresponding two-sided p-value and a 95% confidence interval will be presented. Significance level p-values will be adjusted for multiple comparisons using the FDR method.

In addition, change in amount (mass) of vaginal drug after dosing will also be assessed in CVL in similar fashion. As an explanatory variable, the screening semen sample from the male partner will be used to assess the typical semen biomarker value for each male participant so that the volume of ejaculate can be assessed using the CVL.

Primary Pharmacodynamic Analysis

In order to assess the impact of coitus (and semen) on pharmacodynamics (PD) of luminal drug by measuring the anti-HIV-1 activity in CVL samples, antiviral activity (percent inhibition) will be compared at various visits within each cohort. For Group 1, the difference in mean percent inhibition will be compared between:

1. No gel use with coitus vs. endogenous activity (baseline) (impact of coitus on endogenous activity)

For each group, and dose timing (-1 and -24 hours in Group 1 and -1 and -72 hours in Group 2), the difference in mean percent inhibition will be compared between:

2. Gel use alone vs. endogenous activity (baseline) (PD in absence of coitus)
3. Gel use with coitus vs. endogenous activity (baseline) (PD of product following coitus compared to baseline CVL activity)
4. Gel use alone vs. gel use with coitus (Difference in PD in the absence vs following coitus)
5. Gel use with coitus vs. no gel use with coitus (Group 1 only) (PD of product following coitus compared to post-coitus endogenous activity)

In Group 1, for assessment of the BAT dosing regimen, the difference in mean percent inhibition will be compared between:

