1. Gel use, coitus, and post-coital gel use vs. endogenous activity (baseline) (PD of BAT compared to baseline CVL activity)
2. Gel use, coitus, and post-coital gel use vs. gel use (-1 hour) alone (Difference in PD of BAT compared to absence of coitus and post-coital gel)
3. Gel use, coitus, and post-coital gel use vs. gel use (-1 hour) with coitus (Difference in PD of BAT compared to absence of post-coital gel)
4. Gel use, coitus, and post-coital gel use vs. no gel use with coitus (PD of BAT compared to post-coitus endogenous activity)

Differences will be assessed with the use of the paired t-test or Wilcoxon signed-ranks test, as appropriate.

Secondary Acceptability Analysis

Descriptive statistics will be used to summarize behavioral, adherence, and acceptability data. Behavioral characteristics will be described in terms of the proportion of couples reporting sexual behaviors and practices prohibited during study participation. The adherence to product use will be described among couples in the Multiple Dose Cohort (Group 2) only, and will include assessment of the number and percentage of expected daily doses taken. The perceived acceptability of study procedures and use of the product will be described by the proportion of couples indicating that the product or procedures were found to be acceptable. The proportion of couples willing to take part in a trial of similar design in the future will be calculated. No formal testing will be performed.

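### The primary PD analysis lists 19 paired comparisons with no multiplicity adjustment, although the same section adjusts the primary PK p-values; the chance of a false coitus effect is about 19% to 22%

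*Protocol*

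**What the plan says.** Protocol 10.3 gives the PD hypothesis: "Coitus will not alter the antiviral activity in genital tract secretions following single pre-coital dose, BAT or multiple applications of study product". Section 10.4.2 powers one type of contrast for it, gel with coitus against gel without coitus, in Table 19.

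The PD part of 10.6.2 then lists these comparisons as primary:

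- Group 1 only, without gel: "No gel use with coitus vs. endogenous activity (baseline) (impact of coitus on endogenous activity".
- Three comparisons repeated "For each group, and dose timing (-1 and -24 hours in Group 1 and -1 and -72 hours in Group 2": gel alone against baseline, gel with coitus against baseline, and "Gel use alone vs. gel use with coitus (Difference in PD in the absence vs following coitus".
- One further comparison at the two Group 1 timings: "Gel use with coitus vs. no gel use with coitus (Group 1 only".
- Four BAT comparisons in Group 1, including "Gel use, coitus, and post-coital gel use vs. gel use (-1 hour) alone".

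The list closes with "Differences will be assessed with the use of the paired t-test or Wilcoxon signed-ranks test, as appropriate". No alpha, adjustment or order of testing is given for PD.

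The PK part of the same section says "Significance level p-values will be adjusted for multiple comparisons using the FDR method". That sentence directly follows the one on the nine PK assessments, and the PD part begins after it.

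**The concern.** PK and PD are both primary objectives (3.1). The protocol sets a multiplicity rule for PK and none for PD, and gives no reason for the difference. The coitus question has precedence in 10.3 and 10.4.2 but not in the 10.6.2 list, where it stands level with comparisons that do not concern coitus, such as gel alone against baseline. It is also tested several times without a rule for combining the answers.

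The trial is meant to help explain why CAPRISA 004 and VOICE gave different results (2.1). If one of several unadjusted tests is significant by chance and is reported as a primary finding, it would suggest that coitus impairs the gel when it does not.

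**Working it through.** **Inputs.** 20 evaluable couples per group (10.4). SD of the paired difference in percent inhibition: 20 points (10.4.2). The comparisons are those in 10.6.2.

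**1. Count.**
- Group 1: 1 (coitus without gel) + 4 comparisons × 2 timings + 4 BAT = 13.
- Group 2: 3 comparisons × 2 timings = 6.
- Total: 13 + 6 = 19.
- Testing coitus in the presence of gel: 2 timings × 2 groups = 4. BAT against gel at -1 hour alone makes 5.

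**2. The plan's own figure, and the alpha behind it.** Power of the paired t-test from the noncentral t distribution: 19 degrees of freedom, noncentrality (d / 20) × √20. For d = 10 this is 0.5 × 4.472 = 2.236. Two-sided alpha 0.05 gives 0.565, and all ten rows of Table 19 reproduce to three decimals. One-sided 0.05 gives 0.695 and does not reproduce the table. The tabled power therefore assumes unadjusted two-sided 0.05.

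**3. Chance of at least one false coitus effect.** For k independent tests it is 1 − 0.95^k.
- k = 4: 1 − 0.8145 = 0.185.
- k = 5: 1 − 0.7738 = 0.226.

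The BAT test shares the gel -1 hour visit with another contrast, so the trial was also simulated with visits shared as in the protocol, independent visit residuals, 20 couples per group and at least 32,000 runs. With equal visit variances this gave about 19% for four tests and 22% for five. Halving or doubling the SD of the no-gel visits left these at 18% to 19% and 21% to 22%.

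**4. All 19 comparisons.** Independent: 1 − 0.95^19 = 0.623. Simulated with shared visits: about 0.51 (0.47 to 0.51 across the variance settings). Both require every comparison to be null, including gel against baseline. If gel is active and coitus and the second BAT dose do nothing, seven null comparisons remain and the figure is about 28%.

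**5. After adjustment.** Benjamini-Hochberg over the four or five coitus tests, with coitus truly without effect: about 5% chance of any false finding.

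**6. Power after adjustment.**

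| True difference | Unadjusted 0.05 | BH over five, same effect in all five | Isolated effect, four tests (0.05/4) | Isolated effect, five tests (0.05/5) |
|---|---|---|---|---|
| 10 points | 0.565 | about 0.46 | 0.329 | 0.297 |
| 14 points | 0.844 | about 0.82 | 0.646 | 0.611 |

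At 18 points the tabled 0.968 is not visibly reduced when the effect is in all five contrasts. The isolated-effect figure over four tests is 0.883. The last two columns are lower bounds, because Benjamini-Hochberg never rejects less often than Bonferroni.

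**The case against.** The strongest reply is that a statistical analysis plan usually settles multiplicity, and that plan is not shown. The PD text makes no statement about alpha or about what counts as a positive finding. The FDR sentence may have been meant for nine separate assays, whereas PD has a single endpoint. This is a fair limit, and it is why alpha is called inferred here. But the protocol did not leave multiplicity to a later document. It fixed a rule for one primary objective and none for the other, and an analysis plan written faithfully to it could leave PD unadjusted.

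Second, the coitus contrast is identifiable. It is the one powered in 10.4.2, each comparison carries a label stating its own question, and the design looks for regimen-specific answers. A reader might infer that the plan has no contrast of interest at all, or that differing results at -1 and -72 hours would be a contradiction. Neither is supported. What is open is which group, timing or regimen carries the primary answer, and how the repeated tests are handled.

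Third, a reader might infer a false-positive chance of about 50% for the PD analysis. That holds only if gel has no activity over baseline, contrary to the protocol's premise that antiviral activity follows CVL drug levels (2.6.2). Nor is it a ceiling, since independent tests would give 62%. It does not describe the risk to the coitus question.

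Fourth, a reader might infer that only gel alone against gel with coitus bears on the hypothesis. Section 10.3 names BAT as well, so moving every BAT contrast out of the primary family would leave part of the hypothesis untested.

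Finally, the study hypothesis is no effect, and PD power is already only 56% at 10 points. A stricter threshold makes a non-significant result, which would seem to support that hypothesis, easier to reach. This objection stands, and the fix has to answer it.

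**Conclusion.** The point holds. The protocol adjusts its primary PK tests and leaves 19 primary PD comparisons unadjusted. For the question that it hypothesises and powers, the chance of at least one false coitus effect is about 19% over four tests and 22% over five, roughly four times the nominal level. This rests on two-sided 0.05 per test (inferred from Table 19), 20 couples per group, and coitus truly without effect in every cell.

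This is a phase 1, open-label study sized on PK, and no decision rule is tied to PD p-values. The consequence is over-reading of a coitus effect, not a wrong confirmatory claim. The change is worth making because it is small and uses a method that the protocol already adopts.

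**What to change.** In the PD part of 10.6.2:

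1. Name as primary PD contrasts gel alone against gel with coitus at -1 and -24 hours in Group 1 and at -1 and -72 hours in Group 2, plus BAT against gel at -1 hour alone. State that the BAT contrast combines the effect of coitus with that of a second dose.
2. State the two-sided significance level, and apply the FDR method used for PK to these five p-values.
3. Report the other 14 comparisons as supportive, with estimates and 95% confidence intervals.
4. Report unadjusted 95% confidence intervals for the five primary contrasts as well, and state that a non-significant adjusted result is not evidence that coitus has no effect.

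The cost is a few sentences and no new data. Power is lost mainly for small differences, as tabulated above. FDR also does not hold the chance of any false finding at 5% when some contrasts have real effects; it limits the expected share of false findings, which is the standard that the protocol already accepts for PK.

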3.2 Secondary Objective

1. To assess the acceptability of the MTN-011 trial to male and female participants

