7.3.1 Group 1 – Visit 7b: Post-Coital Sampling/ Final Clinic Visit

The following procedures will occur approximately 2 hours after the coital episode.

Table 9: Group 1- Visit 7b: Post-Coital Sampling/ Final Clinic Visit*

Group 1 Visit 7b: Post-Coital Sampling/ Final Clinic Visit* Male and Female Procedures		
Component	Female Participants	Male Participants
Administrative and Regulatory	
 • Provide reimbursement • Schedule next visit or contact, if indicated • Collect coitus visit data 	
 • Provide reimbursement • Schedule next visit or contact, if indicated
Clinical	
 • Perform a modified physical examination, if indicated* • Perform pelvic exam • Disclose available test results, if indicated* • Treat or prescribe treatment for UTI/RTI/STIs or refer, if indicated • Record/update AEs 	
 • Perform a modified physical examination, if indicated* • Perform genital exam • Disclose available test results, if indicated* • Treat or prescribe treatment for UTI/RTI/STIs or refer, if indicated • Record/update AEs
Behavioral/Counseling	
 • Conduct behavioral assessment • Conduct acceptability assessment • Provide counseling: 
 – HIV pre- post- test – HIV/STI risk reduction 	
 • Conduct behavioral assessment • Conduct acceptability assessment • Provide counseling: 
 – HIV pre- post- test – HIV/STI risk reduction

Group 1 Visit 7b: Post-Coital Sampling/ Final Clinic Visit* Male and Female Procedures			
Component	Female Participants	Male Participants	
Laboratory	Urine	
 • Urine culture, if indicated • Urine NAAT for GC/CT, if indicated 	
 • Urine culture, if indicated • Urine NAAT for GC/CT, if indicated
	Blood	
 • HIV-1 serology • PK 	
 • HIV-1 serology
	Vaginal/ Cervical	
 • Vaginal fluid pH • Rapid Trichomonas test, if indicated • KOH wet mount for candidiasis, if indicated • Wet mount for BV, if indicated • CVL 
 – PK – PD – Semen biomarker • Vaginal and cervical biopsies 
 – PK • Cervical cytobrush 
 PK 	

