7.9.3 Protocol and Product Acceptability Assessment

At the Final Clinic Visit, participants will receive a standardized assessment, which will include questions regarding their experience with trial participation, and whether or not

the participant would be willing to take part in a trial of similar design in the future. They will also be asked about the acceptability of and experience with using the gel.

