10.2.2 Secondary Endpoints

Consistent with the secondary study objective to assess the acceptability of the MTN - 011 trial to male and female participants, the following secondary endpoints will be assessed:

- **Acceptability.** Overall experience with participating in the clinical trial and willingness to participate in a future trial.

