10.5 Participant Accrual, Follow-up and Retention

The accrual and follow-up period will be 6-12 months. More than 20 couples may be enrolled into each group to reach the target of 20 evaluable couples in each group.

A couple is considered evaluable if ALL of the following have been achieved:

- The primary pharmacokinetic endpoints (tenofovir levels from cervicovaginal lavage (CVL) and vaginal/cervical tissue biopsies) are provided at both the visits where the female participants dose with gel and engage in coitus and the visits where female participants dose with gel and do not engage in coitus, and
- At each Gel/Sex Visit, the couple has completed coitus, and
- In Group 2, gel has been used daily at least 5 of the 7 days prior to the study visits

Couples in Group 1 will be followed for approximately 8 weeks and couples in Group 2 will be followed for approximately 14 weeks.

As stated above in the definition of an evaluable couple, to adequately assess the primary PK objective of this study, it is important for each couple to provide complete data throughout follow-up. Thus, target retention should be set at 100%. Once a couple is enrolled in the study, the study site will make every reasonable effort to retain the couple for the entire study period so that they are evaluable.

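### Acceptability is to be summarised per couple, although the objective concerns men and women and each partner answers separately; the questionnaire is also not scheduled for couples who leave early

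*Protocol*

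**What the plan says.** Protocol section 3.2 gives a single secondary objective: "To assess the acceptability of the MTN-011 trial to male and female participants". Section 10.2.2 names the endpoint as "Overall experience with participating in the clinical trial and willingness to participate in a future trial", without a unit of analysis.

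The data are collected from each person. Table 9 (Group 1, Visit 7b) and Table 15 (Group 2, Visit 9) list "Conduct acceptability assessment" in both the female and the male column.

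Under Secondary Acceptability Analysis, section 10.6.2 plans to report the "proportion of couples indicating that the product or procedures were found to be acceptable". For willingness it says: "The proportion of couples willing to take part in a trial of similar design in the future will be calculated". It closes with "No formal testing will be performed".

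On timing, section 7.9.3 says "At the Final Clinic Visit, participants will receive a standardized assessment". Appendices I and II mark the assessment only at Visit 7b and Visit 9 respectively, and neither has a column for early termination. Section 10.5 allows over-enrolment: "More than 20 couples may be enrolled into each group to reach the target of 20 evaluable couples in each group".

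**The concern.** The objective asks about two sets of people, the questionnaire is answered by both, and the planned summary merges them into one unit. Two partners give two answers. When the answers differ, the couple has no value until someone chooses a rule, and the protocol states none. Whichever rule is chosen, a single couple percentage cannot show that one sex found the trial less acceptable than the other.

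A difference by sex is plausible here. Section 5.1.1 itself notes that women have more visits and procedures than men. By Table 16, women give PK lavage, vaginal and cervical biopsies, cytobrush, blood and a rectal sponge at five visits in Group 1 and four in Group 2. Men have no such sampling visits.

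The second, smaller point is who gets asked. With the questionnaire tied to the last scheduled visit, a couple that stops earlier has no scheduled occasion to give an opinion. At stake is how well the trial describes its own acceptability, which matters to anyone planning a similar post-coital study. No efficacy, safety, PK or PD conclusion depends on it.

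**Working it through.** The protocol states no acceptability rate, sample size or precision for this endpoint, so there is no planned figure to reproduce. All rates below are assumptions chosen to show how far the result can move.

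**1. Unit of analysis, section by section**

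- Objective (3.2): male and female participants.
- Endpoint (10.2.2): no unit stated.
- Collection (Tables 9 and 15): each partner.
- Analysis (10.6.2): couple, for both acceptability and willingness.
- Rule turning two answers into one: none stated.

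**2. What a couple figure can be, given the answers by sex**

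Let *f* be the proportion of women willing and *m* the proportion of men. Without assuming how far partners agree, the bounds are:

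- both partners willing: from max(0, *f* + *m* − 1) to min(*f*, *m*);
- at least one partner willing: from max(*f*, *m*) to min(1, *f* + *m*).

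| Assumed women / men | Both willing | At least one willing |
|---|---|---|
| 60% / 90% | 0.60 + 0.90 − 1 = 50%, up to 60% | 90% up to 100% |
| 80% / 80% | 0.80 + 0.80 − 1 = 60%, up to 80% | 80% up to 100% |

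If partners answered independently, the first row would give 0.60 × 0.90 = 54% and 1 − 0.40 × 0.10 = 96%. So the same individual answers can appear as anything from 50% to 100%, depending on the unstated rule and on how often partners agree. Swapping the sexes in the first row leaves every couple figure unchanged: 90% of women with 60% of men gives the same 50–60% and 90–100%. The couple figure therefore cannot show which sex was less willing.

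**3. Early leavers**

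Take one group, 20 women who reach the final visit and 18 of them willing (90%). Assume a dropout fraction *d*, enrol *N* = 20/(1 − *d*) rounded up, and let the missing answers be all unwilling or all willing.

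| Assumed dropout | Enrolled | All leavers unwilling | All leavers willing |
|---|---|---|---|
| 10% | 23 | 18/23 = 78% | 21/23 = 91% |
| 20% | 25 | 18/25 = 72% | 23/25 = 92% |
| 30% | 29 | 18/29 = 62% | 27/29 = 93% |

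The range lies on both sides of 90%. These are extreme bounds, not estimates. They show what is unknown if leavers are not asked, and they do not establish the direction of any error. Sections 5.1.2 and 10.5 target 100% retention, in which case the range closes to 90%.

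**The case against.** The couple is a sensible unit for part of this. Both partners must qualify (sections 7.2 and 7.4), both are terminated if either permanently stops gel use (section 7.6), and a similar future trial could enrol only couples in which both are willing. That argument stands as a reason to keep a couple figure. It supports the both-agree version in particular, which section 10.6.2 does not specify. It does not make the couple figure an answer to an objective about men and women.

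It can also be said that table layout and coding rules belong in an SAP that is not shown. But the protocol does not leave the unit open: it names the couple for both items, and an SAP that follows it inherits the mismatch.

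Three stronger readings are tempting, and the documents support none of them.

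- *A reader might infer that drop-outs are excluded.* Section 10.6.2 does not limit the acceptability summary to completers. The evaluability rule in section 10.5 concerns PK samples, completed coitus and Group 2 gel use. Section 9.8 plans an attempt at a final evaluation for those who leave, section 7.6.3 seeks an Early Termination Visit for the other partner after a report of non-monogamy, and the notes under Tables 9 and 15 name the final and early termination visits together. Those notes concern the return of test results, however, and no text lists the questionnaire among early termination procedures.
- *A reader might infer that the result is biased toward acceptance.* Many exits are required for reasons unrelated to opinion of the trial: HIV infection, STI, pregnancy or reported non-monogamy (sections 7.6.1 to 7.6.3 and 9.3). Leaving because the trial is unacceptable is possible, but the protocol gives no basis for its share.
- *A reader might infer that the objective cannot be answered.* Each partner's answers are recorded, so results by sex can be tabulated from planned data. Disagreement is hidden in the planned summary, not lost from the data.

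**Conclusion.** The point holds at low severity. As written, section 10.6.2 prescribes a per-couple summary that is undefined when partners disagree and does not report by sex, although the objective names both sexes and both are asked. Under assumed rates of 60% and 90%, the couple figure could be anywhere from 50% to 100%. That range rests on assumed rates and on leaving partner agreement unrestricted; close agreement between partners would require similar rates in the two sexes and would narrow it. In addition, the questionnaire is explicitly scheduled only at Visit 7b or Visit 9, so early leavers are not scheduled to be asked; the size and direction of any effect are unknown. The endpoint is secondary, descriptive and untested, and the PK and PD analyses are unaffected.

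**What to change.** - **Section 10.6.2:** for the acceptability and willingness items, report the proportion of female participants and the proportion of male participants separately within each group. Add the proportion of couples in which both partners agree as a supplementary figure, defined as both answering favourably.
- **Section 7.9.3 and Appendices I and II:** list the acceptability assessment at the Early Termination Visit for both partners.
- **Reporting:** state the number of respondents out of all enrolled, by sex and group.

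The first and third changes use data already planned and cost only table layout. The second adds one existing questionnaire at a visit that sites already try to hold. It is the only change that is time-sensitive, because answers not collected when a couple leaves may not be recoverable. No new instrument and no extra participants are needed.
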